1.1 PROTOCOL SUMMARY AND/OR SCHEMA

The purpose of this study is to define if the use of nightly sildenafil after radical prostatectomy results in better erectile function outcomes than nightly placebo for men who have undergone this operation. The study is also designed to compare erectile function outcomes between men using regular sildenafil and those using regular penile injections. Patients undergoing either laparoscopic or open nerve-sparing radical prostatectomy, who meet the inclusion and exclusion criteria, will be asked to participate in the study. Patients will be randomized into one of the three arms:

- 1. PRN Sildenafil Arm: Patients will use sildenafil 100 mg PRN for sexual relations. Patients will take placebo (blinded) at night regularly, except on nights when the sildenafil 100 mg pill is taken. There will be 40 patients in this group.
- 2. Nightly Sildenafil Arm: Patients will use sildenafil 100 mg PRN for sexual relations. Patients will take sildenafil 50 mg (blinded) at night regularly, except on nights when the sildenafil 100 mg pill is taken. There will be 80 patients in this group.
- 3. Combination Therapy Arm: Intracavernous injections of a trimix combination (Papaverine 30 mg/mL, Phentholamine 1 mg/mL, Prostaglandin E1 10 mcg/mL) will be injected three times a week and sildenafil 50 mg taken on the other four (non-injection) nights. Injection therapy can be used for the purposes of sexual relations. There will be 80 patients in this group.

Patients have the option of consenting either preoperatively or up to 6 weeks postoperatively.

Preoperative consent: Patients will be evaluated in the clinic and will complete the questionnaires at baseline (before surgery) and 3, 6, 9, 12, 18, and 24 months postoperatively. At 12 months postoperatively, all patients will stop treatment.

[figure not shown]

(RB PB

IRB#: 09-005 A(10)

Postoperative consent: Patients will be evaluated in the clinic and will complete the questionnaires retrospectively (after surgery) and 3, 6, 9, 12, 18, and 24 months after starting rehab. At 12 months after starting rehab, all patients will stop treatment.

The estimated time to completion of enrollment is 18-24 months. Patients will be monitored for a total of 24 months. Visits 3, 6, 9, 12, 18, and 24 months will have ± 2 week window.

	Baseline	3 Months (±2 weeks)	6 Months (±2 weeks)	9 Months (±2 weeks)	12 Months (±2 weeks)	18 Months (±2 weeks)	24 Months (±2 weeks)
Routine Blood Test	X						
Liver Function Blood Test		X	X	X	X	X	X
Sitting and Standing Blood Pressure and Pulse	X	X	X	X	X	X	X
International Index of Erectile Function Questionnaire (IIEF)	X	X	X	X	X	X	X
Pill Diary/Sexual Encounter Diary		X	X	X	X	X	X
Adverse Event Assessment		X	X	X	X	X	X

IRB PB

IRB#: 09-005 A(10)

2.1 OBJECTIVES AND SCIENTIFIC AIMS

The objective of this study is to analyze the ability of 3 different pharmacological strategies to preserve the ability of men to achieve spontaneous (non-medication assisted) functioning erections after bilateral nerve-sparing radical prostatectomy.

Primary End-Point: Difference in the erectile function (EF) domain score of the International Index of Erectile Function (IIEF) between the 3 groups at 24 months.

Secondary End-Points:

- The time to return of spontaneous functional erections
- The time for patients to respond to oral erectogenic therapy
- The proportion of patients who have normalization of their erectile function (normalization of the EF domain of the IIEF)

3.0 BACKGROUND AND RATIONALE

It is estimated that 10% of all men presenting with erectile dysfunction (ED) suffer the condition, as a result of surgical procedure, typically, radical pelvic surgery. ED is associated with a significant decrease in self-esteem, loss of productivity and relationship discord. Many treatments that restore erectile function have been demonstrated to increase quality of life for both patient and partner. Over the past 10 years there has been a recrudescence in interest in clinical and basic scientific research in post-radical prostatectomy erectile dysfunction. Major discrepancy exists in the literature regarding postoperative potency rates with spontaneous erectile function occurring in 30-80% of patients. Thus, despite the advent of nerve sparing techniques a significant percentage of men continue to suffer from erectile impairment following this operation. It is estimated that 50,000 men undergo radical prostatectomy in the USA alone each year. It has been postulated lately, that the development of transient ED following nerve-sparing surgery due to trauma to the cavernous nerve might trigger a process of damage to the endothelial and smooth muscle cavernous tissue that in turn can induce permanent veno-occlusive ED. Furthermore, preliminary data suggest that the regular erectile activity induced by pharmacological agents may translate into improved preservation of spontaneous erections following bilateral nerve sparing surgery.

Mechanisms of Post-Prostatectomy Erectile Dysfunction

Mechanistically, post-RP ED may be neurogenic, arteriogenic, venogenic, or mixed vascular (arteriovenogenic) in nature. Neurogenic impotence, while obviously occurring after cavernous nerve interruption, may also occur transiently following cavernous nerve traction and/or dissection. Even in the hands of expert nerve sparing surgeons, temporary neural trauma may occur. It is believed that the primary mechanism of development of arteriogenic erectile dysfunction results from transection of the accessory pudendal arteries, and venogenic impotence is based upon corporal smooth muscle collagenization and fibrosis and this is most probably the result of either apoptosis associated with neural injury and/or disuse atrophy. The

IRB PB

IRB#: 09-005 A(10)

venocclusive mechanism is a major determinant of success with vasoactive therapies, indeed, most of the patients failing to respond to erectogenic pharmacologic therapy have venous leak contributing to their ED. The venocclusive mechanism is dependent upon appropriate corporal smooth muscle expansion with resultant occlusion of the subtunical venules. Failure to expand the corporal smooth muscle adequately because of structural alterations in the tissue results in failure to compress the subtunical venules present between the corporal smooth muscle and the tunica albuginea resulting in venous leak. Corporal smooth muscle integrity is believed to be dependent upon 2 factors, cavernosal tissue oxygenation (as occurs during penile erection) and neural integrity (neural injury has been shown to lead to apoptosis and corporal smooth muscle fibrosis).

In previous work, Mulhall et al have examined the chronology of venous leak development post-radical prostatectomy in patients with excellent preoperative erectile function who developed postoperative erectile dysfunction. The incidence of venous leak, (suggestive of permanent, irreversible structural damage to the erectile tissue) was 8% less than four months postoperatively, 22% four to eight months postoperatively and 50% eight to twelve months postoperatively. In this analysis no patient was treated with postoperative pharmacotherapy in any regimented fashion. More recent data, from our clinical database, has indicated that the post-RP penile vascular status is predictive of return of spontaneous erections, degree of erectile rigidity, and response to sildenafil citrate (unpublished to date). The data also indicate that the prognosis is poor for the return of functional erections in the presence of abnormal end diastolic velocity values.

Rationale for the Use of Nightly Viagra Postoperatively

Sildenafil is a PDE5 inhibitor, which has been shown to be effective in men with erectile dysfunction of various etiologies including post-RP. It has also been demonstrated to increase the recovery of erectile function after cavernous nerve injury in human and animal models.

Sildenafil citrate (Viagra) enhances the effects of nitric oxide (NO), a signaling molecule that has a diverse range of physiological effects in many tissues, including promoting relaxation of smooth muscle in the walls of blood vessels and the erectile tissue within the corpora cavernosa of penis. The effect of NO on smooth muscle is mediated by cyclic guanosine monophosphate (cGMP); sildenafil works by inhibiting the enzyme, cGMP-specific phosphodiesterase type 5 (PDE5), that degrades cGMP. Experience has established the role of sildenafil citrate in the treatment of erectile dysfunction (ED). The efficacy of sildenafil for ED post-radical prostatectomy has been studied. In the seminal publication by Goldstein et al, subpopulation analysis suggested a 43% responder rate (GAQ positivity) for this population. Since then in numerous prostatectomy specific studies, sildenafil has been identified as a useful management strategy to facilitate men resuming sexual relations.

A recent Pfizer sponsored study assessed the utility of daily sildenafil citrate administration on the recovery of spontaneous erectile function after radical prostatectomy. In a randomized fashion, 25 men were treated with 50 mg daily, 25 with 100 mg daily and 25 were treated with

IRB PB

IRB#: 09-005 A(10)

placebo. Therapy was instituted at 4 weeks postoperatively and lasted 38 weeks. Analysis was conducted at 48 weeks following RP. The criteria for inclusion were rigorous, patients requiring a combined score of 8 from questions 3 and 4 on the IIEF questionnaire as well as at least one 55% erection on nocturnal penile tumescence and rigidity analysis. Success was defined as preservation of the score of 8 on questions 3 and 4 of the IIEF. No difference was seen in the success rate between the 50 mg and 100 mg arm of the study. However, 27% of men in the treatment arm compared to 4% of men in the placebo arm had preservation of preoperative erectile function. While cavernosal oxygenation may be a contributor to these results, most of these patients did not obtain an erection in response to sildenafil early postoperatively, thus other factors must be at play.

While much of the attention has been focused on corporal smooth muscle in the study of post prostatectomy ED, it is appreciated that the endothelium plays a major role in erection and thus maintaining endothelial health following RP may improve long-term spontaneous erectile function outcome. Desouza et al utilized flow-mediated dilation (FMD) of a transiently occluded brachial arteries as a model assessing nitric oxide dependent endothelial function. In their study, 14 patients with both type II diabetes and erectile dysfunction were enrolled. Following the baseline measurement of brachial artery width patients received 25 mg sildenafil, and an hour later the acute phase FMD was measured. Patients continued sildenafil 25 mg once daily for 14 weeks. 24 hours after the last sildenafil dose chronic phase FMD was measured. In both the acute and chronic phase of treatment patients in the treatment arm had a significantly greater FMD than the placebo-controlled group, thus indicating that sildenafil enhanced endothelial function. The positive effects of sildenafil on endothelium has been confirmed in men with cardiovascular disease. In the laboratory of [name], daily administration of sildenafil in the rat model of cavernous nerve crush injury has resulted in better preservation of endothelial staining (using CD31 immunohistochemistry) and reduction in apoptotic indices (on TUNEL assay). Unpublished data from Pfizer indicates that sildenafil has a positive impact on the PI3/AKT/eNOS pathway.

Rationale for the Use of Regular Intracavernosal Injections Postoperatively

The relationship between hypoxia and cavernosal fibrosis has been documented in several studies (11), it is thought that hypoxia induces TGF-beta1 that in turn accelerates collagenization of the corpus cavernosum smooth muscle, while at the same time, decreasing the level of PGE1 that help protect from fibrosis (12). Since, hypoxia of cavernous tissue is related to the blood supply and the greatest blood supply occur at time of erection any neural damage that results in ED may expose the cavernous tissues to longer periods of hypoxia. Leungwattanakij et al (13) demonstrated in a cavernous neurotomy rat model that sharp neural injury resulted in an increase in hypoxia inducible factor-1 (HIF-1alpha) and TGF-beta1 as well as increase in cavernous tissue collagen synthesis. In a landmark study, Montorsi et al (5) based a study on the assumption that the events of nocturnal erection supply the cavernous bodies with oxygenation that might protect them from developing fibrotic changes during the transient period of erectile dysfunction following nerve sparing radical prostatectomy. In their study they treated patients with 3 weekly intracavernousal injections of Alprostadil. This in

IRB PB

IRB#: 09-005 A(10)

turn would ensure that when the erectile function would resume the secondary fibrotic changes to the penile tissue would not be sever enough to cause erectile dysfunction on their own. In this prospective study 30 patients were enrolled, all potent, all had nerve-sparing RP. 15 received 3 weekly injections for 15 weeks. 12 completed the treatment. Although the trial was small, the difference between treatment and control group was statistically significant. (Treatment group - 67% had erections sufficient for intercourse versus. 20% in the Control group - p < 0.01) However, to date this is the only randomized evidence supporting the role of penile rehabilitation with intracavernosal injections after radical prostatectomy. There is a need for a larger confirmatory study particularly using a modality that avoids intracavernosal injections. Intracavernosal injection therapy was originally discovered in 1983. In 1985, trimix, in the form of papaverine/phentolamine/prostaglandin E1 was introduced. It is efficacious in approximately 90% of patients with ED.

4.1 OVERVIEW OF STUDY DESIGN/INTERVENTION

4.2 Design

Patients undergoing either laparoscopic or open nerve-sparing radical prostatectomy, who meet the inclusion and exclusion criteria described in section 6.0, will be asked to participate in the study. Patients will be randomized into one of three arms and assigned a study number from CRDB (unrelated to their medical record number):

- life according to their ability; patients interested in using medication for sexual activity, will be offered sildenafil 100 mg to be used before intercourse on an asrequired basis. They will be given six 100 mg doses, per month, for a 12 month duration. Each patient in this group will use a placebo pill (blinded) each night, except on a night that 100 mg is taken for the purpose of sexual relations. This group can be considered to constitute "usual care" as it represents the current approach to penile rehabilitation in the community. We estimate, in the first 3 months, most people will not use sildenafil at all, after this, probably no more than once per week on average. The total expected dose in the PRN group is about 4000 mg over the course of the year. There will be 40 patients in this group.
- 2. Nightly Sildenafil Arm: Patients will be instructed to take sildenafil 50 mg (blinded) at night regularly, even when intercourse is not planned. These patients will be instructed to take 100 mg pill on occasions that they are interested in sexual relations. On these occasions, they will forego the usual nightly pill. They will be given six 100 mg doses, per month, for a 12-month duration. There will be 80 patients in this group.
- **3.** Combination Therapy Arm: Intracavernous injections of a trimix combination (Papaverine 30 mg/mL, Phentholamine 1 mg/mL, Prostaglandin E1 10 mcg/mL) will be injected three times a week, and sildenafil 50 mg taken on the other four

IRB PB

IRB#: 09-005 A(10)

(non-injection) nights. Injection therapy can be used for the purpose of sexual relations. There will be 80 patients in this group.

Preoperative consent: Patients will be evaluated in the clinic and will complete the questionnaires at baseline (before surgery) and 3, 6, 9, 12, 18 and 24 months after surgery. At 12 months postoperatively, all patients will stop treatment. Visits 3, 6, 9, 12, 18, and 24 months will have ± 2 week window.

Postoperative consent: Patients will be evaluated in the clinic and will complete the questionnaires retrospectively (after surgery) and 3, 6, 9, 12, 18 and 24 months after starting rehab. At 12 months after starting rehab, all patients will stop treatment. Visits 3, 6, 9, 12, 18, and 24 months will have ±2 week window.

4.3 Blinding

Preoperative consent: Patients are to be consented and registered as pending prior to their surgery. Full registration and randomization will occur immediately following surgery, if nerve bundles have been spared.

Postoperative consent: Patients may also consent to the study up to 6 weeks postoperatively at which point they will be registered and randomized immediately following informed consent in clinic.

The blind 50 mg pills will be taken last thing at night, before the patient goes to bed without sexual stimulation (100 mg will be used for sexual relations). Thus, the chances of a man having an erection that would "unblind" him is remote. Furthermore, in the first 9 months after surgery, very few men will respond to any PDE5 inhibitor medication because of the intra-operative transient nerve injury. Finally, it takes on average, one hour before an erection can occur, and this must be in the setting of sexual stimulation. Thus, the patient will likely be asleep at this time. Hence, we believe that patients will remain blinded to whether they are on active or placebo sildenafil. Nonetheless, blinding will be assessed at the end of the study.

4.4 Intervention

Three interventions are to be used:

1. PRN Sildenafil Arm: Patients will be instructed to take placebo QHS (blinded) except on nights that they are interested in sexual relations, they will then be instructed to use sildenafil 100 mg (open-label) and skip the placebo dose. Placebo will start within 24-48 hours after registration. There will be 40 patients in this group.

(RB PB

IRB#: 09-005 A(10)

- 2. Nightly Sildenafil Arm: Patients will be instructed to take sildenafil 50 mg QHS (blinded) except on nights that they are interested in sexual relations, they will then be instructed to use sildenafil 100 mg (open-label) and skip the 50 mg dose. Sildenafil treatment will start within 24-48 hours post-surgery. There will be 80 patients in this group.
- 3. Combination Therapy Arm: Trimix combination (Papavarine 30 mg/mL, Phentholamine 1 mg/mL, Prostaglandin E1 10 mcg/mL), at initial dose of 5 units (0.05 mL) will be given; the first 2 injections will be done in the MSKCC urology outpatient clinic (if needed, the investigator can determine appropriate amount of injections for patient training). The patients will be instructed, by the sexual medicine nurse practitioner, on the technique of injection and dose titration, as well as the limitations, contra-indications, side effects and alternatives. The dosing data will be entered into electronic medical record or patient medical record by the NP. The dose being used cannot be altered by a patient. For safety reasons all dose adjustments are conducted by phone with the NP.

For the first 2 weeks after registration, patients will use nightly sildenafil 50 mg before commencing penile injections 2 weeks (± 3 days) later. Sildenafil treatment will start within 24-48 hours after registration. Patients will inject three times per week and use sildenafil 50 mg on the other four nights. In this arm, patients will be instructed to obtain 3 penetration hardness ($\geq 60\%$ rigidity) erections per week. There will be 80 patients in this group.

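### The diary endpoint for unaided erections needs drug-free encounters, but section 4.4 instructs both oral arms to take sildenafil 100 mg for sex and other sections word this differently

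*Combined protocol and SAP*

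**What the plan says.** **The endpoint.** Section 2.1 makes erections without medication the objective and lists time to their return as a secondary endpoint. Section 14.3 (secondary endpoint 4) takes that time from the diary and compares arms by log rank, with no further definition. Section 10.0 describes the diary as a record of sexual encounters, including whether sildenafil or an injection was used, the dose, penetration and rigidity.

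**The 100 mg pill in year one.** The sections differ:

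- Section 4.4, nightly arm: on nights when "they are interested in sexual relations, they will then be instructed to use sildenafil 100 mg (open-label) and skip the 50 mg dose".
- Section 4.4, PRN arm: on such nights "they will then be instructed to use sildenafil 100 mg (open-label) and skip the placebo dose".
- Section 4.2, nightly arm: "These patients will be instructed to take 100 mg pill on occasions that they are interested in sexual relations".
- Section 4.2, PRN arm: "patients interested in using medication for sexual activity, will be offered sildenafil 100 mg". The start of this bullet is missing from the text available.
- Section 1.1, both oral arms: "Patients will use sildenafil 100 mg PRN for sexual relations".
- Section 4.3 says, in passing, that the 100 mg dose is the one used for sexual relations.

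Supply in both oral arms is limited: "They will be given six 100 mg doses, per month", for 12 months.

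**The combination arm.** "Patients will inject three times per week and use sildenafil 50 mg on the other four nights" (section 4.4). Injections may also serve for sex.

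**After month 12.** Regular treatment stops. On-demand drug for sex is permitted, not instructed (section 10.0).

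**The concern.** An encounter with 100 mg on board cannot show that a man has regained erections without drug. If every encounter before month 12 is medicated, a man who recovered at month 5 and one who recovered at month 11 are both first recorded after month 12. No analysis can recover the lost dates.

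This matters because endpoint 4 is the only listed endpoint that names spontaneous erections, which are the stated objective. Where both oral arms share the instruction, a true speed-up from nightly sildenafil would be shrunk and the log-rank test would lose power. Where the arms are told different things, as section 4.2 reads, the chance of catching an unaided encounter could itself differ by arm.

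**Working it through.** **1. The plan's own figure.** Section 4.2 expects little 100 mg use in the PRN arm for three months, then "probably no more than once per week on average", and about 4000 mg over the year. Nine months is 52.18 × 9/12 = 39.1 weeks, and 39.1 × 100 mg = 3,914 mg, so the figure reproduces. Supply is 6 × 12 = 72 doses.

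**2. Does supply force unaided encounters?** With e encounters a month, the unaided share u is at least 1 − 6/e. At e = 8 that is 25%. At e = 6 or fewer there is no bound. Weekly encounters (52.18/12 = 4.3 a month) can all be medicated.

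**3. Inputs for the size.** From the documents: 80 v 40 men, two-sided 2.5%, treatment to month 12, follow-up to month 24. Assumed, because the documents give no figure:

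- one encounter a week;
- u the same in both oral arms in year one;
- half of year-two encounters unaided;
- recovery times uniform over 9 months, with PRN 3 months later than nightly;
- for power, 70% v 55% of men recovering (inside the 30–80% range in section 3.0).

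**4. Delay for one man.** The mean extra wait to the first unaided encounter is 1/u − 1 weeks: 1 week at u = 50%, 3 at 25%, 9 at 10%, 19 at 5%. At u = 0 nothing is recorded until treatment stops.

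**5. Recorded gap at u = 0.** Recorded time is max(t, 12). Means by recovery window:

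- months 3–12: 12.0
- months 6–15: 12 × 6/9 + 13.5 × 3/9 = 12.5
- months 9–18: 12 × 3/9 + 15 × 6/9 = 14.0
- months 12–21: 16.5

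A true 3-month gap is therefore recorded as 0.5 (3 v 6), 1.5 (6 v 9) or 2.5 (9 v 12) months.

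**6. Other values of u.** Gaps for u > 0 are simulated with 400,000 men per arm. The share of year-one recoveries recorded in year one is 1 − (1/m) × Σ(1−u)^k, k = 1 to m, with m = 39, 26 or 13 weeks. Power is simulated with 6,000 trials per cell (error about 1.3 points). Each triplet is for recovery starting at month 3 / 6 / 9 (in the nightly arm for gap and power).

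| Unaided share u | Recorded gap, months | Recorded in year one | Log-rank power |
|---|---|---|---|
| 0% | 0.5 / 1.5 / 2.5 | 0% | 42 / 54 / 61% |
| 5% | 1.9 / 2.1 / 2.6 | 58 / 46 / 29% | not run |
| 10% | 2.4 / 2.5 / 2.7 | 77 / 68 / 48% | 60 / 61 / 64% |
| 25% | about 2.9 in all | 92 / 88 / 78% | not run |
| 50% | 3.0 in all | 97 / 96 / 92% | 63 / 63 / 64% |

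From u = 50% to u = 0 the loss is 63 − 42 = 21, 63 − 54 = 9 and 64 − 61 = 3 points. From 50% to 10% it is 3, 2 and 0. A repeat of the month-9 case with 4,000 trials per cell gave 63.9% with none unaided and 62.9% with half, so no detectable loss. If 80% recover in both arms and only timing differs, power is 10 / 25 / 35% at u = 0 and 38 / 38 / 37% at u = 50%.

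Setting the year-two unaided share to 100% or 25% moves the gaps by at most about 0.16 months.

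**7. If coaching followed section 4.2.** Suppose recovery is identical in both arms from month 6, with u = 0 in the nightly arm and 10% in the PRN arm. Then 0% of the nightly arm's year-one recoveries are recorded in year one, against 68% of the PRN arm's. In that example the distortion runs against nightly sildenafil.

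**The case against.** **PRN means as needed.** Section 1.1 uses the term for both oral arms, and section 4.2 offers the pill only to interested men in the PRN arm. The sentences in 4.4 can be read as a substitution rule: if 100 mg is taken, skip the bedtime pill. This stands in part. Unaided encounters are possible, and optional use is stated for the PRN arm. But 4.4 says instructed for both arms and 4.2 repeats it for the nightly arm, so the text does not settle which applies.

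**The diary separates medicated from unmedicated encounters**, and 4.4 speaks only of nights. True. The problem is too few informative encounters, not misclassification.

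**Appendices B and F are not in the text.** They may define a spontaneous erection or advise unaided attempts. This stands, and the fix allows for it. Section 10.0 lists no such item.

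**The harm is small where it is most plausible.** Section 4.3 expects few men to respond to this drug class in the first nine months, which points to the later window, where the loss is 3 points or nil. This stands.

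**Different coaching is unlikely.** The bedtime pill is blinded between the oral arms, and arm-specific instructions would work against that. This stands as a reason for doubt, but it is also a reason to use one wording.

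**Stronger readings a reader might infer.** One is that section 9.0 never lets a robust responder go below 25 mg; its down-titration is an example, not a floor. Another is that year-one recovery cannot be observed at all; that needs full compliance and about six or fewer encounters a month.

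**Conclusion.** The point holds as a minor one. Endpoint 4 depends on unmedicated encounters, and the sections give inconsistent instructions about medication for sex during the 12 treatment months. To the extent the stricter wording is followed, year-one recovery is recorded late. If 4.2 were applied literally, detection could also differ between nightly and PRN.

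The size cannot be fixed from the documents, because the unaided share is not given. Under the stated assumptions the power loss is large (21 points) only with recovery from month 3 and near-complete compliance. It is small or nil if recovery starts around month 9 or about 10% of encounters are unaided.

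Two further inferences are not supported. With a shared instruction, the result is attenuation of a true nightly-v-PRN difference, not a false positive. And no direction can be given for comparisons with the combination arm, which has drug scheduled on all seven nights and may inject for sex. The primary endpoint, the erectile function score at 24 months, is unaffected: the instruction ends at month 12.

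**What to change.** (a) In sections 4.2 and 4.4, use one wording for both oral arms: the 100 mg pill is optional for sexual relations and replaces the bedtime pill only when it is used. State that on-demand injection for sex is likewise optional in the combination arm, with the rehabilitation schedule unchanged.

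(b) Unless Appendix B already has it, add one dated diary or visit item, identical in all arms: the first erection hard enough for penetration with no on-demand pill or injection that day and before that night's study pill. Define endpoint 4 on it in section 14.3.

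(c) Add a supporting comparison, in all randomised men, of the proportion recording an unaided functional erection in months 12 to 24, when regular treatment has stopped.

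**Cost.** Some matching text, one item and one analysis. Dosing, sample size and the primary analysis do not change. Under (b), the previous night's active dose may have a residual effect in the nightly and combination arms that placebo cannot have; (c) is there for that reason. Optional wording permits an unaided attempt but does not guarantee one, and on-demand drug remains allowed in year two, so such attempts stay the patient's choice. Endpoint 3 (response to sildenafil) needs medicated encounters, so the wording should permit the 100 mg pill without discouraging it.
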